## 11. Data Quality Assurance

To ensure accurate, complete, and reliable data, Lilly or its representatives will do the following:

- provide instructional material to the study sites, as appropriate
- sponsor start-up training to instruct the investigators and study coordinators. This session will give instruction on the protocol, the completion of the CRFs, and study procedures.
- make periodic visits to the study site
- be available for consultation and stay in contact with the study site personnel by mail, telephone, and/or fax
- review and evaluate CRF data and use standard computer edits to detect errors in data collection
- conduct a quality review of the database

In addition, Lilly or its representatives will periodically check a sample of the patient data recorded against source documents at the study site. The study may be audited by Lilly or its representatives, and/or regulatory agencies at any time. Investigators will be given notice before an audit occurs.

To ensure the safety of participants in the study, and to ensure accurate, complete, and reliable data, the investigator will keep records of laboratory tests, clinical notes, and patient medical records in the patient files as original source documents for the study. If requested, the investigator will provide Lilly, applicable regulatory agencies, and applicable ERBs with direct access to original source documents.

### 11.1. Data Capture System

An electronic data capture system will be used in this trial. The site maintains a separate source for the data entered by the site into the sponsor-provided electronic data capture system.

Case report form data will be encoded and stored in a clinical trial database.

Any data for which the paper documentation provided by the patient will serve as the source document will be identified and documented by each site in that site's study file. Paper documentation provided by the patient may include, for example, a paper diary to collect patient-reported outcome (PRO) measures (eg, a rating scale), a daily dosing schedule, or an event diary.

Bioanalytical data will be stored electronically in the bioanalytical laboratory's database. Data will subsequently be transferred from the bioanalytical laboratory to the Clinical Laboratory Results Modernization system.

Data from complaint forms submitted to Lilly will be encoded and stored in the global product complaint management system.

## 12. Sample Size and Statistical Methods

### 12.1. Determination of Sample Size

The primary objective of this study is to compare abemaciclib plus NSAI versus placebo plus NSAI in terms of PFS in postmenopausal women with HR+, HER2- locoregionally recurrent or metastatic breast cancer.

The key secondary objective of this study is to compare abemaciclib plus fulvestrant versus placebo plus fulvestrant with respect to PFS for postmenopausal women with HR+, HER2- locoregionally recurrent or metastatic breast cancer.

The study plan is to enroll approximately 450 patients in total, with 300 HR+, HER2- locoregionally recurrent or metastatic breast cancer patients who have not received prior endocrine therapy in Cohort A and 150 HR+, HER2- locoregionally recurrent or metastatic breast cancer patients in Cohort B. Assuming approximately 10% screening failure, the study will enter approximately 500 patients.

The approximate 300 patients qualified for Cohort A will be randomized in a 2:1 ratio to Arm A1 (abemaciclib plus NSAI; 200 patients) and Arm A2 (placebo plus NSAI; 100 patients). Patients will be randomized using the following stratification factors: nature of disease (visceral metastases vs. non-visceral metastases) and prior (neo)adjuvant endocrine therapy (prior therapy with disease-free interval > 12 months from completion of treatment vs. prior therapy with disease-free interval ≤ 12 months from completion of treatment vs. no prior therapy).

A 2-look group-sequential design of the primary endpoint will be used to accommodate an event-driven plan for the interim and primary PFS analyses (see Section 12.2.6 for details). The primary PFS analysis will be performed after approximately 170 PFS events in Cohort A have occurred (ie, approximately 43% censoring rate). Assuming a hazard ratio of 0.626, this sample size yields about 81.40% statistical power to detect superiority of the abemaciclib plus NSAI arm over the placebo plus NSAI arm with the use of a 1-sided log-rank test and a type I error of 0.025. If the true median PFS for the placebo plus NSAI arm is 14.4 months, then the hazard ratio of 0.626 amounts to an approximately 8.6-month (59.7%) improvement in median PFS for the abemaciclib plus NSAI arm under an additional assumption of exponential survival distribution.

Approximately 150 patients will be randomized in a 2:1 ratio to Arm B1 (abemaciclib plus fulvestrant; 100 patients) and Arm B2 (placebo plus fulvestrant; 50 patients). Patients will be randomized using the following stratification factors: nature of disease (visceral metastases vs. non-visceral metastases) and sensitivity to endocrine therapy (primary resistance vs. secondary resistance).

The design of Cohort B is to ensure 100 patients' exposure of abemaciclib plus fulvestrant and to show 50% of the global study JPBL trial effect size with roughly 80% probability (ie, 80% of chance to observe a hazard ratio less than 0.824, assuming a true hazard ratio of 0.703 by study assumption).

Here, the effect size of the drug is defined as:

$$\delta = \frac{1}{HR} - 1 = \frac{1 - HR}{HR} = \frac{MST_{Test} - MST_{Control}}{MST_{Control}}$$

$MST_{Test}$  and  $MST_{Control}$  are median survival time in test drug group and control drug group, respectively; effect size can be regarded as the percent change of median survival time.

## 12.2. Statistical and Analytical Plans

### 12.2.1. General Considerations

Statistical analysis of this study will be the responsibility of Lilly.

Efficacy analyses will be based on the intention-to-treat (ITT) analysis set. This population is defined as all patients randomized to study treatment. Patients will be grouped according to randomized treatment.

Safety analyses will be based on the randomized and treated population (ie, Safety Population), defined as all randomized patients receiving at least 1 dose of blinded study drug or NSAID/fulvestrant. Patients will be grouped according to treatment received in Cycle 1.

Pharmacodynamic and/or biomarker analyses will be based on the subset of patients from the above populations from whom a valid assay result (according to laboratory guideline) has been obtained.

All tests of treatment effects will be conducted at a 2-sided alpha level of 0.05, unless otherwise stated. All confidence intervals (CIs) will be given at a 2-sided 95% level, unless otherwise stated.

Any change to the data analysis methods described in the protocol will require an amendment ONLY if it changes a principal feature of the protocol.

Before sponsor unblinding of the aggregate database, minor modifications or clarifications to the data analysis methods may be described and justified in the SAP.

Any other change to the data analysis methods described in the protocol, and the justification for making the change, will be described in the clinical study report (CSR).

The assumptions for each statistical method may be evaluated. If there is violation of assumptions, alternative statistical methods may be used.

Additional exploratory analyses of the data will be conducted as deemed appropriate.

### 12.2.2. Patient Disposition

A detailed description of patient disposition will be provided. It will include a summary of the number and percentage of patients entered into the study, enrolled in the study, and treated, as well as the number and percentage of patients completing the study or discontinuing (overall and by reason for discontinuation).

All patients entered in the study will be accounted for in the summation. The number of patients who do not qualify for analysis, who die, or who discontinue before treatment begins will be specified.

A summary of all important protocol deviations will be provided.

### **12.2.3. Patient Characteristics**

Patient characteristics will include a descriptive summary, by treatment arm, of the following:

- patient demographics
- baseline disease characteristics
- preexisting conditions
- historical illnesses
- prior (neo)adjuvant endocrine therapy
- prior (neo)adjuvant chemotherapy (including both cytotoxic and targeted agents)
- prior endocrine therapy
- prior chemotherapy (including both cytotoxic and targeted agents)

Other patient characteristics will be summarized as deemed appropriate.

### **12.2.4. Concomitant Therapy**

Concomitant medication will be summarized by treatment arm in a frequency table listing the terms recorded on the eCRF.

#### **12.2.4.1. Postdiscontinuation Therapy**

The numbers and percentages of patients reporting postdiscontinuation therapies will be provided overall, by type of therapy (surgery, radiotherapy, or systemic therapy), and by drug name.

### **12.2.5. Treatment Compliance**

The number of dose omissions, reductions, and delays, cycles received, and dose intensity will be summarized for all treated patients per treatment arm.

Treatment compliance information for abemaciclib will be collected through capsules counts at each tumor assessment visit. The estimate of percent compliance will be given by:

$$\text{Percent Compliance} = \frac{\text{Actual cumulative dose taken}}{\text{Expected cumulative dose to be taken}} \times 100$$

The actual cumulative dose taken will be determined based on counting the number of capsules returned at each visit and subtracting that number from the number of capsules dispensed. The expected cumulative dose to be taken will be determined based on the assigned dose and taking into account any dose reductions or omissions.

### 12.2.6. Primary Outcome and Methodology

The primary endpoint of this study is PFS in Cohort A. Progression-free survival time is measured from randomization until the date of objective progression as defined by RECIST v1.1, or death from any cause. Patients who have neither progressed nor died will be censored at the day of their last radiographic tumor assessment, if available, or date of randomization if no post-initiation (ie, post-baseline) radiographic assessment is available. The detailed censoring rules are described in [Table JPBQ.12.1](#).

**Table JPBQ.12.1. Rules for Determining Date of Progression or Censor for Progression-Free Survival**

Rule	Situation	Date of Progression or Censor	Outcome
1	No baseline tumor assessments	Date of randomization	Censored
2	No post-baseline assessments and no death	Date of randomization	Censored
3	No documented progression and no death (with a post-baseline tumor assessment)	Date of last adequate tumor assessment	Censored
4	Patient lost to follow-up (or withdrew consent from study participation) before documented progression or death	Date of last adequate tumor assessment	Censored
5	Documented progression	Date of documented progression.  If a tumor assessment was done on multiple days, use the earliest date for that visit.	Progressed
6	Death without documented progression	Date of death	Progressed
7	Documented progression or death after missing $\geq 2$ consecutive post-baseline tumor assessments	Date of last adequate tumor assessment before missed assessments or date of randomization, whichever is later.	Censored

Note: Progression-free survival and associated outcome is determined by the earliest of the dates above, if more than 1 situation applies.

The PFS analysis to test the superiority of abemaciclib plus NSAI to placebo plus NSAI in improving PFS time will use the stratified log-rank test stratified by nature of disease (visceral metastases vs. non-visceral metastases) and prior (neo)adjuvant endocrine therapy (prior therapy with disease-free interval > 12 months from completion of treatment vs. prior therapy with disease-free interval  $\leq$  12 months from completion of treatment vs. no prior therapy). The Kaplan-Meier method (Kaplan and Meier 1958) will be used to estimate the PFS curves, as well

as PFS rates at every 3 months for each treatment group. These rates will be compared based on a normal approximation for the difference between the rates.

A group-sequential design of the primary endpoint will be used to accommodate an event-driven plan for the interim and primary analysis. One interim analysis will be conducted by the DMC after approximately 119 (corresponding to 70% information rate) PFS events have been observed. The purpose of the interim analysis is to provide early efficacy information and allow for potential early communication with regulatory agencies. The O'Brien Fleming alpha spending function (Lan and DeMets 1983) will be used to preserve the overall type I error.

Therefore, if the interim analysis is performed after exactly 119 events have been observed, a 1-sided p-value of less than 0.0082 (corresponding approximately to an observed hazard ratio <0.627 under an exponential model) will need to be observed to declare statistical significance (see [Table JPBQ.12.2](#)).

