**Table JPBQ.12.2. Properties of Design for Progression-Free Survival**

Information Fraction	Cumulative Events	Cumulative Alpha Spent	Cumulative Beta Spent	Boundary Reject $H_0$ (1-sided p-value)
0.70	119	0.0082	0	<0.0082
1	170	0.0250	0.2	<0.0223

The actual alpha spent will be calculated based on the actual number of events observed at the time of analysis using software that implements the alpha-spending function noted above (eg, ADDPLAN 6.0 or SAS 9.2).

If the interim analysis crosses the boundary of significance at the pre-specified level, the study is considered positive. If statistical significance is not declared at the interim, the final PFS analysis will be conducted with approximately 170 PFS events. All remaining alpha will be spent at the final analysis on Cohort A. Once statistical significance is declared at either interim analysis or the final analysis, the study is considered positive.

The Cox proportional hazard model (Cox 1972) with treatment as a factor will be used to estimate the hazard ratio and corresponding 95% CI with Wald's test p-value after stratifying for the same randomization variables specified for the primary analysis.

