### **12.2.14. Interim Analysis and Other Planned Analyses**

An interim analysis on Cohort A will be conducted by the DMC after approximately 119 PFS events have been observed. The interim analysis will be conducted to provide early efficacy information and could potentially result in early communication with regulatory agencies. The O'Brien Fleming alpha spending function (Lan and DeMets 1983) will be used to preserve the overall type I error. If the analysis of PFS is significant using the cutoff described in Section 12.2.6, the DMC will be instructed to engage the SMD, who may subsequently convene an IRC to propose actions based upon the DMC's recommendation. All patients will continue

follow-up for PFS until study completion, and will remain blinded for the duration of the study unless emergency unblinding (Section 9.5.2) are met. If Cohort A show early efficacy at interim, the sponsor may consider early stop, unblinding and crossover for this cohort; however, regulatory agencies will be consulted before any action is taken.

The unblinded analysis, including review of the efficacy along with the safety data, will be conducted by the DMC. Only the DMC is authorized to evaluate unblinded interim efficacy and safety analyses. Study sites will receive information about interim results ONLY if they need to know for the safety of their patients.

If statistical significance is not declared at the interim, a final analysis of Cohort A will be conducted with about 170 PFS events.

The interim analysis of Cohort B is triggered only if statistical significance is declared at the Cohort A interim analysis. No DMC is required for the analysis of Cohort B. The analysis will provide both safety and efficacy information of Cohort B and could potentially result in early communication with regulatory agencies, including consultation of potential decisions regarding early stop, unblinding and crossover before any action is taken.

In the case of early stop and crossover for Cohort A or Cohort B after the interim analysis, Lilly will notify investigators when the crossover begins.

If patients in Cohort A continue being followed for PFS until final analysis, the final analysis of Cohort B will be conducted at the same time of Cohort A final analysis. If Cohort A stops early at interim due to efficacy, the final analysis of Cohort B may be conducted after approximately 105 PFS events have been observed in Cohort B.

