### 6.7.1.2. Hypotheses and Analysis

Letting  $S_A(t)$  and  $S_P(t)$  denote the progression free survival functions of Abemaciclib + NSAI and placebo + NSAI respectively, the null hypothesis

$$H_0: S_A(t) = S_P(t)$$

will be tested against the one sided alternative hypothesis

$$H_1: S_A(t) > S_P(t).$$

There is 1 planned interim analysis and 1 primary analysis to test these hypotheses. At each analysis, the hypotheses above will be tested using a one sided stratified log rank test, stratified by nature of disease and prior (neo)adjuvant endocrine therapy.

The interim analysis is planned to take place after approximately 119 (70%) investigator assessed PFS events have occurred. The cumulative 1-sided type I error rate of .025 will be maintained using the O'Brien Fleming boundary.

Therefore, if the interim analysis is performed after exactly 119 events have been observed, a 1-sided p-value of less than 0.0082 (corresponding approximately to an observed hazard ratio <0.627 under an exponential model) will need to be observed to declare statistical significance (see Table JPBQ.6.2).

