**Table JPBQ.6.2. Properties of Design for Progression-Free Survival**

Information Fraction	Cumulative Events	Cumulative Alpha Spent	Cumulative Beta Spent	Boundary Reject $H_0$ (1-sided p-value)
0.70	119	0.0082	0	<0.0082
1	170	0.0250	0.2	<0.0223

The actual alpha spent will be calculated based on the actual number of events observed at the time of analysis using software that implements the alpha-spending function noted above (for example, ADDPLAN 6.0 or SAS 9.2).

If the interim analysis crosses the boundary of significance at the pre-specified level, the study is considered positive. If statistical significance is not declared at the interim, the final PFS analysis will be conducted with approximately 170 PFS events. All remaining alpha will be spent at the final analysis on Cohort A. Once statistical significance is declared at either interim analysis or the final analysis, the study is considered positive.

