## 6.13. Interim Analyses and Data Monitoring

An interim analysis will be conducted under the auspices of a DMC according to the specifications set forth in the protocol.

An interim analysis on Cohort A will be conducted by the DMC after approximately 119 PFS events have been observed. The interim analysis will be conducted to provide early efficacy information and could potentially result in early communication with regulatory agencies. The O'Brien Fleming alpha spending function (Lan and DeMets 1983) will be used to preserve the

overall type I error. If the analysis of PFS is significant using the p-value boundary described in Section 6.7.1.2, the DMC will be instructed to engage the SMD, who may subsequently convene an IRC to propose actions based upon the DMC's recommendation. All patients will continue follow-up for PFS until study completion, and will remain blinded for the duration of the study unless emergency unblinding (Protocol Section 9.5.2) are met. If Cohort A show early efficacy at interim, the sponsor may consider early stop, unblinding and crossover for this cohort; however, regulatory agencies will be consulted before any action is taken.

The unblinded analysis, including review of the efficacy along with the safety data, will be conducted by the DMC. Only the DMC is authorized to evaluate unblinded interim efficacy and safety analyses. Study sites will receive information about interim results ONLY if they need to know for the safety of their patients.

At the time of the interim analysis, analyses of PFS provided to the DMC will include:

- the boundary values for significance based on the exact number of observed events,
- the p-value for a stratified log rank test comparing the two treatment arms, stratified by the randomization factors,
- an estimate of the HR between the two arms based on a Cox proportional hazards model, stratified by the randomization factors, and
- a KM analysis by treatment arm.

Safety evaluation will be based, at least, on the following data reports:

- summary of patient discontinuations and reasons for discontinuation
- summary of SAEs
- Lilly Safety System reports for all patients with SAEs
- summary of TEAEs

Details pertaining to the conduct of these analyses are provided in the JPBQ DMC Charter.

If statistical significance is not declared at the interim, a final analysis of Cohort A will be conducted with about 170 PFS events.

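### The printed Cohort A boundaries (1-sided 0.0082 and 0.0223) do not come from the alpha-spending function the plan names, which gives 0.0074 and 0.0228

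*Protocol*

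**What the plan says.** Cohort A has one interim PFS analysis at about 119 events and a final analysis at about 170, with 1-sided type I error 0.025.

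- **Method named.** Protocol 12.2.6: "The O'Brien Fleming alpha spending function (Lan and DeMets 1983) will be used to preserve the overall type I error". Protocol 12.2.14 and SAP 6.13 name the same function with the same citation.
- **Interim threshold.** Protocol 12.2.6 presents the threshold at exactly 119 events as a consequence of that choice: "a 1-sided p-value of less than 0.0082 (corresponding approximately to an observed hazard ratio <0.627 under an exponential model". SAP 6.7.1.2 repeats it.
- **Tables.** Protocol Table JPBQ.12.2 and SAP Table JPBQ.6.2 both print 0.0082 at information fraction 0.70 and 0.0223 at the final analysis.
- **Recalculation.** Under its table, the protocol says the alpha actually spent will be computed from the observed event count "using software that implements the alpha-spending function noted above (eg, ADDPLAN 6.0 or SAS 9.2". The SAP says the same under its own table, and SAP 6.13 has the DMC receive "the boundary values for significance based on the exact number of observed events".
- **A second method name.** SAP 6.7.1.2: "The cumulative 1-sided type I error rate of .025 will be maintained using the O'Brien Fleming boundary".
- **Final analysis.** "All remaining alpha will be spent at the final analysis on Cohort A".

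**The concern.** The classical O'Brien-Fleming boundary and the Lan-DeMets spending function of O'Brien-Fleming type are related, but they give different critical values at a finite number of looks. The plan names the second and prints the numbers of the first.

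At exactly 119 events, an interim p between 0.0074 and 0.0082 is significant by the tables and not by the named function. At 170 events, a p between 0.0223 and 0.0228 is the reverse. Crossing at the interim makes the study positive. It also triggers the Cohort B interim, which is descriptive, and lets the sponsor consider early stop, unblinding and crossover after consulting regulators. A threshold with those consequences should not leave a choice of reading once the data are seen.

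**Working it through.** **Inputs.** 119 and 170 events, so t = 119/170 = 0.70 (Protocol 12.1 and 12.2.6); 1-sided alpha 0.025, design hazard ratio 0.626, 2:1 allocation and stated power 81.40% (Protocol 12.1). The two test statistics are taken as bivariate normal with correlation √0.70. The hazard ratio cutoff is exp(−z·√(4.5/events)), where 4.5 = 1/(2/3 × 1/3).

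**1. Reproducing the printed figures: classical O'Brien-Fleming boundary.** Here z at information fraction t is c/√t, with c chosen so that total alpha is 0.025.
- c = 2.0080; interim z = 2.0080/√0.70 = 2.400.
- Interim p = 0.00820; cutoff exp(−2.400 × √(4.5/119)) = 0.627.
- Final p = 0.02232.
- Drift under hazard ratio 0.626 is −ln(0.626) × √(170/4.5) = 2.879, which gives power 81.42%.

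Both p-values, the hazard ratio cutoff and the stated power are reproduced.

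**2. The named function.** Alpha spent at t is 2[1 − Φ(z₀.₉₈₇₅/√t)].
- 2[1 − Φ(2.2414/√0.70)] = 2[1 − Φ(2.679)] = 0.00738.
- Interim z = 2.438; cutoff exp(−2.438 × √(4.5/119)) = 0.622.
- Solving for total alpha 0.025: final z = 2.000, p = 0.02275. Power is 81.5%.

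Neither printed p-value nor the printed cutoff is reproduced. This function does not spend 0.0082 until about 122 events (t = 0.719). Other spending functions tried at t = 0.70 do not give 0.0082 either: power family ρ = 3 gives 0.0086 and ρ = 2 gives 0.0122; Hwang-Shih-DeCani γ = −4 gives 0.0072 and γ = −3 gives 0.0094; a 2-sided 0.05 function halved gives 0.0096.

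**3. Side by side.**

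| | Printed | Classical boundary | Named function |
|---|---|---|---|
| Interim p, 119 events | 0.0082 | 0.0082 | 0.0074 |
| Interim hazard ratio cutoff | 0.627 | 0.627 | 0.622 |
| Final p, 170 events | 0.0223 | 0.0223 | 0.0228 |
| Power at hazard ratio 0.626 | 81.40% | 81.4% | 81.5% |
| Chance of crossing at interim, hazard ratio 0.626 | not given | 50.3% | 48.8% |

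**4. How often it matters.**
- Interim p falls between the two thresholds: 1.5% of trials under hazard ratio 0.626, 0.08% under the null.
- Under hazard ratio 0.626, about 95% of those trials are still positive at 170 events by the named function.
- Overall verdict differs under hazard ratio 0.626: 0.080% positive only by the classical boundary plus 0.199% positive only by the named function, 0.28% in all. Under the null: 0.039% + 0.039% = 0.08%.

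**5. Type I error.** The printed pair gives a total of 0.02498. Spending 0.0082 and then all remaining alpha gives a final level of 0.0223. Only a mix of the printed interim with the other method's final level (0.0082 with 0.0228) exceeds the limit, at 0.0254.

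**6. Other event counts.** This step assumes the classical constant is re-solved at each information fraction, which neither document provides for. Named function against classical is then 0.0069 and 0.0078 at 117 events, 0.0079 and 0.0086 at 121, and 0.0084 and 0.0090 at 123.

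**The case against.** The strongest reply is that the plan already says which rule operates. The interim comes at approximately 119 events, the 0.0082 is conditional on exactly 119, and both documents require recalculation with the spending function. On that reading the tables only illustrate the design. This narrows the conflict but does not remove it: at exactly 119 events the required software returns 0.0074, while the text and both tables state 0.0082 for that same count.

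A second reply is that the tables are not miscalculated. They form one coherent classical design, and SAP 6.7.1.2 names a boundary of that kind. That is fair, and it is why either the name or the numbers could be corrected. But SAP 6.7.1.2 is then at odds with SAP 6.13 and with the sentence under its own table.

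Third, the effect is small and the rule on remaining alpha excludes the one mix that would exceed 0.025. That stands, and it limits the severity. The comparison away from 119 events does rest on an assumed rule. The DMC Charter, to which SAP 6.13 refers for details, was not available and may already fix the method; it would still have to agree with the protocol and SAP.

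**Conclusion.** The concern holds. The printed boundaries belong to the classical O'Brien-Fleming design, and the method named in Protocol 12.2.6, Protocol 12.2.14 and SAP 6.13 gives 0.0074 and 0.0228. No statement gives one precedence over the other. This is an inconsistent decision threshold and not inflation of type I error. It should be fixed because the interim rule can declare the study positive, although the practical effect is small. The figures assume exactly 119 and 170 events, a 1-sided 0.025 level, the usual normal approximation for the log-rank statistic and, for power and hazard ratio cutoffs, 2:1 allocation.

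**What to change.** Settle one method in both documents before the unblinded interim.

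- **Option 1, the simpler, because recalculation with the spending function is already required.** Keep the Lan-DeMets function. Change the interim entries in Tables JPBQ.12.2 and JPBQ.6.2 (cumulative alpha and boundary) and the accompanying text to 0.0074, with hazard ratio <0.622, and the final boundary to 0.0228. Replace the boundary wording in SAP 6.7.1.2 with the same function, and restate power as about 81.5%. The interim hurdle becomes slightly stricter: the chance of crossing under hazard ratio 0.626 is 48.8% instead of 50.3%.
- **Option 2, equally valid.** Keep every printed number, name the classical O'Brien-Fleming boundary throughout, and replace the spending-function recalculation with a stated rule for event counts other than 119.

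In either case, check that the DMC Charter uses the same method. The cost is wording and table edits, with no extra patients or events and almost no change in overall power.
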